7. To be able to differentiate the impact of the TSC condition and the impact of the everolimus treatment on growth and sexual development a data set from peri-pubertal patients with TSC, who have not been exposed to everolimus will be used as a reference. These patients are a subset of the patient population that is currently being enrolled into the TOSCA registry (CRAD001MIC03). By end of enrollment TOSCA will have collected the data of approximately 1700 patients from 31 countries around the world. The descriptive analyses will present, side by side, the results from the CRAD001M2305 patients and those from the TOSCA registry patients not treated with an mTOR inhibitor, whenever similar data are collected in both studies. Detailed definition of the TOSCA subset of patients that will be used as a TSC-untreated reference population is provided in this amendment. If the missing data pattern is not limiting, exploratory indirect comparisons between patients treated by everolimus (from M2305 study) and those who never received an mTOR inhibitor (TOSCA subset of patients) will be performed to evaluate the everolimus effect on growth and sexual development (through the use of propensity scores).

8. The WHO growth charts will be used as reference data representing the average global population. Since no weight-for-age references are available from the WHO above 10 years of age, the WHO BMI-for-age references from 0 to 19 years of age will be used and the BMI standard-deviation scores (SDS) will be analyzed instead of weight SDS.
9. The long-term brain development and in particular the occurrence of TSC associated neurocognitive disorders will be assessed through the collection of the TAND Checklist, whenever available. Brain MRI scans may be evaluated, provided that scientific or technological advancements allow these data to be used for assessing brain functions.
10. The window to allow patients entering the study was extended from 3 to 6 months after end of treatment in study CRAD001M2301.
11. The language regarding evaluation of adverse event data was aligned with Novartis data directory requirements.

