#### 1.1.1 SEGA-associated with TSC

TSC is an autosomal dominant genetic disorder caused by inactivating mutations in the *TSC1* or *TSC2* genes, with a prevalence ranging from 1 in 6000 to 1 in 25,000 (Morrison 2009, Crino 2006, Osborne 1991). TSC affects approximately 1 million people worldwide (Anon 2010). The disease is characterized by benign, highly vascular, hamartoma growth and variable clinical manifestations ranging from mild dermatologic findings to seizures (which affect up to 90% of patients), learning disabilities (38% to 80%), mental retardation (50% to 70%), autism (20% to 60%), and fatal renal, cardiac, or pulmonary diseases (Curatolo 2002, Levine 2006).

Despite this broad range of clinical findings, a limited number of features are responsible for the morbidity and decreased life expectancy associated with this disease. These include neurologic disorders such as SEGAs and seizures, renal diseases such as angiomyolipomas and renal cell carcinoma (RCC), pulmonary disease (lymphangiomyomatosis), and cardiovascular disease (rhabdomyoma) (Goh et al 2004).

The incidence of SEGA in TSC varies from 5 to 15% (Shepherd et al 1991). SEGA lesions are usually associated with TSC. They arise in the subependymal layer of the lateral ventricle and are usually located near the foramen of Monro and enhance homogeneously with contrast on MRI with no evidence of surrounding edema. These are slow-growing lesions that are typically unapparent clinically until they reach sufficient size to produce ventricular obstruction and hydrocephalus. By the time symptoms are noted, they are often irreversible even by emergent surgical intervention. They arise deep within the brain in the region of the foramen of Monro, which hampers their surgical resection, as the approach to the lesion entails removal of substantial amounts of viable cerebral tissue. Surgery, even when successful, often results in significant morbidity.

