#### **1.2.1.2 Clinical experience**

##### **Interventional studies in patients with tuberous sclerosis complex:**

Everolimus has been investigated in one phase I/II study (28 patients) in patients with TSC who have SEGA [CRAD001C2485]. Additionally, two phase III studies have been conducted in patients with TSC: study [CRAD001M2301] in patients with TSC who have SEGA (117 patients) and study [CRAD001M2302] in patients with renal angiomyolipoma

(118 patients). [CRAD001MIC02] is an ongoing, expanded access phase IIIb study for patients with TSC associated SEGA. Currently there is a fourth phase III study [CRAD001M2304] ongoing in which everolimus will be tested to evaluate whether its use as adjunctive treatment results in reducing seizure frequency in patients with TSC who have refractory seizures.

Data on a small series of TSC patients who had systematic SEGAs which were treated with daily rapamycin therapy showed tumor size reduction by 46-63% within 2.5 to 5 months (Franz et al 2006). All lesions exhibited regression and, in one case, necrosis. Interruption of therapy for one patient resulted in regrowth of the SEGA, but further regression of another 62-75% was seen upon the resumption of therapy. These results represented a new therapeutic paradigm for the treatment of SEGAs in the TSC patients with rapamycin and related agents.

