**Table 1-1 Non-interventional studies**

Non interventional studies			
Study no.	CRAD001MIC03	CRAD001MCO05	CRAD001M1401
Title	TOSCA	Epidemiological follow-up	Survey
Population	Patients, any age with TSC diagnosed within last 12 months	Patients with confirmed diagnosis of TSC	TSC Patients <15-years-old
Study design	International, observational disease registry, retrospective and prospective	Epidemiological, monographic registry model with open follow-up, retrospective and prospective; competitive recruitment	Observational, site survey; patient registration

For additional efficacy and safety information, please refer to the most recent edition of the Investigator’s Brochure as well as the Afinitor/Votubia prescribing information.

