## **2.2 Rationale for the study design**

CRAD001M2305 is a prospective, multi-center phase IIIb/IV study. This study will investigate if the physical and sexual development of pediatric patients is affected by previous or ongoing treatment with everolimus.

Growth (height, weight), sexual development (Tanner Stages, sex hormone levels, age at menarche, thelarche (females) and adrenarche (males)), and brain development (assessed by TAND Checklist, dates of brain MRI) of patients participating in this long-term follow-up study will be followed at annual visits to the site until patients achieve Tanner Stage V or age 16 (females), age 17 (males) whichever occurs first.

Adverse events, concomitant medication, appearance of menarche, will be monitored and data collected every 3 months (“3-monthly”). As per local product information, all patients should be receiving periodic Therapeutic Drug Monitoring (TDM) to monitor the blood trough concentration of everolimus, any available everolimus blood trough levels with date of sample collection, will be recorded every 3-months. Unless clinically indicated these 3-monthly visits can be performed per telephone.

Of note: the participation in this study does not require the administration of everolimus. In such cases in which the patient is taking everolimus, data collection (such as TDM, trough level, duration of everolimus interruptions and everolimus prescribed dose) will only be recorded, when available. Everolimus treatment, should it be continued during CRAD001M2305, will be based on the local product information.

Blood samples will be collected annually for assessment of endocrine levels at a local lab for all patients, starting at age 10 until study participation is ended.

Data collected in this CRAD001M2305 study will be pooled with the corresponding patient's data collected in the parent CRAD001M2301 study, in particular background information on the disease history, demographics and baseline characteristics, everolimus exposure, sexual and growth development data.

To facilitate the interpretation of the CRAD001M2305 results and help differentiate the impact of the TSC condition versus the impact of everolimus on growth and sexual development, a descriptive statistical comparison will be performed using data from patients with comparable clinical characteristics, enrolled in the TOSCA registry and not treated with an mTOR inhibitor.

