2.3.1 Full Analysis Set

In order to describe data from the CRAD001M2305 patients and those from the TOSCA registry side by side, the following analysis sets will be used.

- The Full Analysis Set (FAS):
 - for CRAD001M2305, FAS will consist of all patients enrolled in the CRAD001M2305 study.
 - for TOSCA, FAS will consist of all patients enrolled in this TOSCA registry whose age at study entry was below 16 (for female) and 17 (for male) years and who never received an mTOR inhibitor throughout the registry follow-up period nor recorded as prior or ongoing treatment at the baseline visit.
- The Full Analysis Set for sexual development (FAS Puberty):
 - for CRAD001M2305, FAS Puberty will consist of the FAS patients defined above.
 - for TOSCA, FAS Puberty will consist of the FAS patients defined above but restricting from the patients to those aged between 9 to 17 years (for, females 9 to 16 years, males 9 to 17 years) at registry entry. The TOSCA registry is designed to collect Tanner Staging until 2017 (i.e. 4 to 6 years of follow-up). Thus it is considered adequate to select only TOSCA patients aged between 9 to 17 years old at the time of entry to the registry to allow for obtaining puberty data corresponding to the peri-pubertal time frame.

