4.2 Indirect Comparison Analysis

Confidence interval was so wide even for 1 patient with growth development abnormality as shown below in the table 1-1. Estimation was not robust due to the small sample size. Sample size of 15 patients is too small for any comparison, Considering the unlikelihood of making a robust analysis with the limited enrolment into CRAD001M2305, indirect comparison is not meaningful.

Table 1-1 95% confidence interval for different number of observed patients with growth development abnormality during M2305

Number of patients with growth development abnormality	Sample size N = 50		Sample size N = 15	
	Rate of patients with growth development abnormality	Exact binomial 95% confidence interval	Rate of patients with growth development abnormality	Exact binomial 95% confidence interval
0	0.00	(0.00, 0.07)	0.00	(0.00, 0.22)
1			0.07	(0.00, 0.32)
2	0.04	(0.00, 0.14)	0.13	(0.02, 0.40)
3			0.20	(0.04, 0.48)
4	0.08	(0.02, 0.19)	0.27	(0.08, 0.55)
5			0.33	(0.12, 0.62)
6	0.12	(0.04, 0.24)	0.40	(0.16, 0.68)
7			0.47	(0.21, 0.73)
8	0.16	(0.07, 0.29)	0.53	(0.27, 0.79)
9			0.60	(0.32, 0.84)
10	0.20	(0.10, 0.34)	0.67	(0.38, 0.88)
11			0.73	(0.45, 0.92)
12	0.24	(0.13, 0.38)	0.80	(0.52, 0.96)
13			0.87	(0.60, 0.98)
14				
	0.28	(0.16, 0.42)	0.93	(0.68, 0.998)

5 Appendix

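### The TOSCA reference sets carry no SEGA criterion and no planned table shows their SEGA mix, so the side-by-side display leaves SEGA-related differences mixed with everolimus, mainly for Tanner V, endocrine values and post-baseline SDS.

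*SAP*

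**What the plan says.** **Treated group.** All M2305 patients come from the parent trial, described in Protocol 1.2.1.2 as "study [CRAD001M2301] in patients with TSC who have SEGA (117 patients").

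**Reference group.** TOSCA is a general TSC registry; Protocol Table 1-1 gives its population as "Patients, any age with TSC diagnosed within last 12 months". SAP 2.3.1 sets the rule: "for TOSCA, FAS will consist of all patients enrolled in this TOSCA registry", subject to an age limit by sex and no mTOR inhibitor before or during follow-up. FAS Puberty adds a lower age limit of 9. Neither set mentions SEGA.

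**Promise and purpose.** Protocol 2.2 says that "a descriptive statistical comparison will be performed using data from patients with comparable clinical characteristics". SAP Section 1 says the display should help tell the impact of TSC from that of everolimus. SAP 2.2 is more modest: it speaks of describing a potential everolimus impact within the TSC population. Protocol 2.1 itself raises TSC, SEGA and non-everolimus therapy as possible influences on growth and sexual development.

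**Adjustment.** Type of TSC lesions appears in SAP 3.9.3, in the list used to look for imbalance before a propensity score might be built. SAP 4.2, citing 15 enrolled patients, concludes that "indirect comparison is not meaningful". SAP Section 1, 3.9 and 3.9.3 still carry the comparison, conditional on sufficient numbers, and Table 2-2 still has a row for it.

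**Tables.** The baseline summary in SAP 3.2 names age, sex, race, weight, height and BMI. Subgroups in SAP 3.12 are by exposure duration, in M2305 only. SAP 3.8.1 adds counts by region.

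**The concern.** The two columns differ in at least two respects at once: everolimus exposure and SEGA. SDS standardises for age and sex, and endocrine values are shown by gender and age, but nothing in the retained tables accounts for SEGA. Nor could a reader of those tables see how many reference patients have it.

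The display serves the primary endpoints of a safety study requested by a regulator. If children with SEGA grow or mature differently without any drug, the difference could be read as harm from everolimus, or could hide harm if it runs the other way. Confidence intervals convey the random error of 15 patients; they do not convey this.

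**Working it through.** **1. The SAP's reason for giving up the comparison.** SAP 4.2 rests on exact (Clopper–Pearson) intervals at N = 15. Recomputed, 0/15 gives an upper limit of 0.218 (printed 0.22), and 1/15 gives 0.0017 to 0.3195 (printed 0.00, 0.32). All 15 rows at N = 15 reproduce. At N = 50, seven of eight rows do; for 6/50 the lower limit is 0.0453 against 0.04 printed, a rounding slip of no consequence. The judgement that 15 patients are too few for modelling is numerically sound.

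**2. How much of a SEGA gap stays in the display.** Let p1 be the untreated level (a rate or a mean SDS) with SEGA, p0 the level without, and s the SEGA share of the reference.

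- Reference level: s·p1 + (1 − s)·p0
- M2305 level with no drug effect: p1
- Displayed difference: (1 − s)(p1 − p0)

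The only figure for s is TSC-wide, from Protocol 1.1.1: "The incidence of SEGA in TSC varies from 5 to 15" percent. The share in the TOSCA sets is not given, so 30% and 50% are added as assumptions. The gaps in the last two columns are also assumptions, for scale only.

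| s | fraction of gap left | rates 5% without, 10% with SEGA | SDS gap of 0.3 |
|---|---|---|---|
| 5% | 95% | 10 − 5.25 = 4.75 points | 0.285 |
| 15% | 85% | 10 − 5.75 = 4.25 points | 0.255 |
| 30% | 70% | 10 − 6.5 = 3.5 points | 0.21 |
| 50% | 50% | 10 − 7.5 = 2.5 points | 0.15 |
| 100% | 0% | 0 | 0 |

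The formula treats SEGA as present or absent, with M2305 patients like other SEGA patients.

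**3. What the pre-drug baseline already shows.** For height and BMI, SAP 2.1.4 and Table 2-1 take the M2305 baseline on or before the start of everolimus. If the SEGA offset is a constant d and s does not change over follow-up:

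- difference at Baseline: (1 − s)d
- difference at Year k: (1 − s)d
- difference in change from baseline: (1 − s)d − (1 − s)d = 0

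If the offset moves from d0 to dk, (1 − s)(dk − d0) remains in the change. A stable offset is therefore visible before any drug. It misleads only a reader who compares post-baseline levels alone, and SAP 3.8.1 specifies summaries by year without naming change from baseline.

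This protection is weaker elsewhere. SAP 2.1.5 says some patients have no endocrine or Tanner assessment before everolimus, so their baseline is the first later one. Reaching Tanner V by age 16 or 17 is a single end result with no baseline value to subtract.

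**4. What a SEGA subset could offer.** Protocol Amendment 1 gives the registry's size: "By end of enrollment TOSCA will have collected the data of approximately 1700 patients from 31 countries". At 5–15% that is 0.05 × 1700 = 85 to 0.15 × 1700 = 255 SEGA patients, before the age and mTOR restrictions and missing data. With an assumed SD of 1:

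- M2305 mean alone: 1.96/√15 = 0.51 SDS
- difference against 85: 1.96·√(1/15 + 1/85) = 0.55 SDS
- difference against 255: 1.96·√(1/15 + 1/255) = 0.52 SDS
- difference against 25, if the restrictions cut that deep: 0.64 SDS

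The 15 M2305 patients limit precision whatever reference is used.

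**The case against.** The strongest reply is that the study is descriptive, plans no tests on percentage rates, and has 15 patients. Height and BMI are also read against WHO norms and a pre-drug baseline. On assumed inputs, a spurious 0.26–0.29 SDS is about half the half-width of the M2305 mean alone. A general TSC reference also fits the SAP 2.2 wording, and SAP 3.9.3 already warns about unobserved covariates.

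Much of that stands and limits the point. It does not explain why SEGA status is missing from the baseline summary, or why SAP Section 1 still claims the display helps separate disease from drug.

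Three stronger readings are tempting, and the documents do not support them.

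- *A firm adjustment for SEGA has been cancelled.* The propensity score was always exploratory, to be used only if imbalances mattered and if deemed relevant. SAP 4.2 calls the comparison not meaningful, but other sections keep it. That is an inconsistency, not a clean cancellation.
- *85–95% of a known SEGA effect will appear as a drug effect.* No SEGA effect on growth is quantified, its direction is unknown, and 5–15% is not the share in the TOSCA sets.
- *A SEGA-only reference would solve the problem and should be the primary one.* Protocol 1.1.2 dates approval of everolimus for SEGA needing intervention to 2010–2011. Registry patients with SEGA who never received an mTOR inhibitor are therefore a selected group and may have milder disease. Making them primary would exchange one confounder for another.

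**Conclusion.** The point holds in limited form. The reference is not matched on SEGA, the planned summaries do not show its SEGA mix, and the promise of comparable clinical characteristics is not carried out for disease features. The display therefore mixes SEGA with everolimus, chiefly for Tanner V, endocrine values, and post-baseline SDS levels or trajectories. The fraction of any SEGA gap left in is 1 − s: 85–95% if the registry mirrors the protocol's TSC-wide figure, 70% or 50% at an assumed share of 30% or 50%. The gap itself cannot be sized from the documents. A reader might infer that no difference in the display can be interpreted; for height and BMI SDS the pre-everolimus baseline row prevents so broad a conclusion. This is a worthwhile correction to make before database lock, not a fault that invalidates the study.

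**What to change.** - Tabulate SEGA status and type of TSC lesions at baseline for both studies, on FAS and FAS Puberty.
- Beside the all-TOSCA column, add a supplementary column, with its n, for TOSCA patients with recorded SEGA: height SDS and BMI SDS on FAS, Tanner V on FAS Puberty. Include endocrine tables only where the gender-by-age cells are large enough. Do not name this column the primary reference, and state that its patients are selected.
- Show change from the pre-everolimus baseline for height and BMI SDS.
- In SAP Section 1, replace *differentiate* with the descriptive language of SAP 2.2, and state the residual confounding by SEGA.
- Reconcile SAP 4.2 with SAP Section 1, Table 2-2, 3.9 and 3.9.3, so that the SAP says once whether the indirect comparison will be run.

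**Cost.** A few table rows, one extra column, change-from-baseline summaries and text edits. The work assumes that TOSCA records SEGA in usable form; the documents show only lesion type as a planned covariate. The SEGA subset will be small, selected and imprecise, and the 15 M2305 patients stay the limiting number. The column reduces this confounding without removing it.

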## 4 Study design

### 4.1 Description of study design

This is a prospective, multi-center, long-term follow-up, Post-Authorization Safety Study (PASS) evaluating the growth and development of pediatric patients who are currently being treated with everolimus or who have previously been treated with everolimus for TSC-associated SEGA in [CRAD001M2301]. The study will include all consenting pediatric patients who at the time of completion of study CRAD001M2301 have not achieved Tanner Stage V and are younger than 16 years (for females) or 17 years (for males), and were receiving treatment with everolimus in study [CRAD001M2301] within 6 months before enrollment into CRAD001M2305.

According to [CRAD001M2301] enrollment figures, it is anticipated that at the time of the start of study CRAD001M2305, approximately 50 patients may be eligible for this study, if they consent to participate.

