The dates of all performed brain MRI scans that are done in the scope of the regular TSC SEGA follow-up will be collected at the annual visits. Brain MRI data will not be collected at this point but may be retrieved at a later date if technological advancements pertaining to predicting future cognitive abilities such as the development of the working memory arise.

Brain development will be assessed by determining the occurrence of TSC-Associated-Neuropsychiatric-Disorders (TAND) with an appropriate TAND Checklist at each annual visit.

The first study visit will occur 3 months after enrollment in CRAD001M2305 and the first annual visit one year ( $\pm 30$  days) after enrollment in CRAD001M2305. The 3-monthly visits can be performed per telephone unless a visit to the site is clinically indicated.

Patient participation in the study will be completed once the patient has achieved Tanner Stage V or age 16 for females, age 17 for males, whichever occurs first.

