### 5.3 Exclusion criteria

1. Pediatric female patients who were on study treatment in CRAD001M2301 and have not reached Tanner Stage V but are within 3 month of turning age 16  
or
2. Pediatric male patients who were on study treatment in CRAD001M2301 and have not reached Tanner Stage V but are within 3 months of turning age 17
3. Any patient who was pregnant prior to start of CRAD001M2305

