2.1 Definitions

2.1.1 Date of first administration of everolimus

For CRAD001M2305 patients, the date of first administration of everolimus is defined as the first date when a non-zero dose was administered in the parent study CRAD001M2301. This date was recorded on Study History (HIS) Case Report Form (CRF) of the CRAD001M2305 study.

For the sake of simplicity, the date of first administration of everolimus will also be referred to as the *start of everolimus*.

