3.8.1 Height and BMI

For CRAD001M2305 patients, all data described below will be pooled with the corresponding data from Study CRAD001M2301.

The height standard deviation score (SDS) will be calculated based on height data collected during the study and published reference height information. The height SDS (also called z-score) will be computed for a particular patient at each time point. The same approach will be used to compute BMI SDS. BMI will be calculated as weight (in kg) / squared height (in m). The z-scores will allow identification of potential outliers.

SDS will be calculated using the current formula provided by the WHO as follows:

1. Calculate $z_{ind} = \frac{\left(\frac{X}{M}\right)^L - 1}{LS}$
2. If $|z_{ind}| \leq 3$, $SDS = z_{ind}$
If $z_{ind} > 3$, $SDS = 3 + (X - SD3pos) / SD23pos$
If $z_{ind} < -3$, $SDS = -3 + (X - SD3neg) / SD23neg$

where:

- X is height in centimeters or BMI in kilograms/m²,
- L , M and S are height or BMI-, sex- and age-specific reference values from the WHO Growth Charts.
- $SD3pos$ is the cutoff 3SD calculated by the LMS method:
 $SD3pos = M * (1 + LS*3)^{1/L}$

- $SD3neg$ is the cutoff -3SD calculated by the LMS method:
 $SD3pos = M * (1 + LS*(-3))^{1/L}$
- $SD23pos$ if the difference between the cutoffs 3SD and 2SD:
 $SD23pos = M * (1 + LS*3)^{1/L} - M * (1 + LS*2)^{1/L}$
- $SD23neg$ if the difference between the cutoffs -2SD and -3SD:
 $SD23neg = M * (1 + LS*(-2))^{1/L} - M * (1 + LS*(-3))^{1/L}$

Height-for-age and BMI-for-age L, M and S reference values for boys and girls are available under [<http://www.who.int/childgrowth/standards/en/>] (for patients aged between 0 to 5 years old) and [<http://www.who.int/growthref/en/>] (for patients aged between 5 to 19 years old). These correspond to the latest available international references available at the time of this protocol and described in the 2007 Bulletin of the World Health Organization (Mercedes de Onis et al 2007). However, these references may be revised according to new available standards at the time of the analysis.

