The age category immediately above the patient's exact age should be used. SDS is actually a Z score that measures the distance from the population mean in units of standard deviations. That is, $SDS < 0$ refers to values lower than the population mean, and for example $SDS \leq -1.645$ refers to values in the lowest 5%. (The usual percentile more commonly used in the clinical practice can be derived from the Z-score by a normal distribution).

The time-course of height and BMI SDS will be summarized, side by side, on the FAS of the studies CRAD001M2305 and TOSCA using descriptive statistics by year since the enrollment date (for TOSCA patients) or since the start of everolimus (for CRAD001M2305 patients). The counts and frequencies of patients with height and BMI SDS values lower than the 5th percentile (notably low) or higher than the 95th percentile (notably high) will be described on the FAS, overall and by region. The counts and frequencies by region will be provided if sufficient sample size observed within the region for CRAD001M2305 study.

The rate of height (respectively BMI) growth notable abnormality will be calculated as the rate of patients with a height $SDS < 5$ th percentile at the last time point where height is reported.

If the number of CRAD001M2305 patients is sufficient and if a high rate of notably height (respectively BMI) growth abnormality occurs, the relationship between the everolimus exposure and the height growth abnormality will be further explored as detailed below:

- The rate of height (respectively BMI) growth abnormality will be described in the different subgroups defined by the duration of everolimus exposure. These subgroups are described in the Section 3.12.
- The duration of exposure and the age at start of everolimus will be summarized using descriptive statistics in the subgroups of patients with and without a height (respectively BMI) growth abnormality.
- A logistic regression including the duration of exposure and the age at the start of everolimus as continuous covariates will also be used to further explore the relationship between the everolimus exposure and the height (respectively BMI) growth notable abnormality. Additional covariates (e.g. time normalized Cmin) might also be included in the model.

In addition, individual patient graphs for height and BMI over time will be provided for CRAD001M2305 patients.

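### The 16/17 age limit acts at Day 1 in TOSCA but after Day 1 in M2305, and only M2305 has a stated end at Stage V or 16/17, so the side-by-side height and BMI SDS rows cover different ranges of attained age and maturity

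*SAP*

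**What the plan says.** SAP 2.3.1 defines the TOSCA Full Analysis Set as "all patients enrolled in this TOSCA registry whose age at study entry was below 16 (for female) and 17 (for male) years", with no mTOR inhibitor received. Registry enrolment is Study Day 1 for these patients (SAP 2.1.3). The restriction to ages from 9 years belongs to FAS Puberty and does not apply to height and BMI.

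For M2305, "FAS will consist of all patients enrolled in the CRAD001M2305 study". Eligibility (Protocol 4.1) covers children who "at the time of completion of study CRAD001M2301 have not achieved Tanner Stage V and are younger than 16 years (for females"; the sentence goes on to give 17 years for males. Protocol 5.3 also excludes boys who "are within 3 months of turning age 17", with a matching rule for girls and age 16. The M2305 clock starts elsewhere: the start of everolimus is "the first date when a non-zero dose was administered in the parent study CRAD001M2301" (SAP 2.1.1), and that date is Treatment Day 1.

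SAP 3.8.1 shows height and BMI SDS side by side "by year since the enrollment date (for TOSCA patients) or since the start of everolimus (for CRAD001M2305 patients". It also takes the rate of notable abnormality at each patient's last reported height.

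Participation in M2305 "will be completed once the patient has achieved Tanner Stage V or age 16 for females, age 17 for males" (Protocol 4.1, Monitoring). For TOSCA, SAP 2.1.6.1 says only that growth data come at baseline and annually if available. The 4 to 6 years of follow-up in SAP 2.3.1 is stated for Tanner staging.

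**The concern.** The same age figures are used in both groups but at different points on the time axis. TOSCA can contain a child just under 16 or 17 at Day 1. M2305 can contain such a child only if the interval from first dose to the end of M2301 is close to zero. M2305 children must also still be short of Stage V at that later date and leave on reaching it; nothing comparable is stated for TOSCA.

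Height and BMI SDS by year since baseline are primary endpoints (Protocol 3), and SAP 1 gives the TOSCA column the job of helping to separate the effect of TSC from that of everolimus. The planned propensity step would have considered age and Tanner stage at baseline (SAP 3.9.3), but SAP 4.2 now calls the indirect comparison not meaningful. That leaves the unadjusted rows. A reader could take a difference between columns as a drug effect when part of it comes from who is eligible to be in each row.

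**Working it through.** **1. The plan's own figure.** The plan quantifies only precision. SAP 4.2 gives 0.07 (0.00, 0.32) for 1 abnormality in 15 patients. Clopper-Pearson: lower limit 1 − 0.975^(1/15) = 0.002; upper limit, the 0.975 quantile of Beta(2, 14), = 0.319. This reproduces.

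**2. Where each rule acts.**

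| | TOSCA | M2305 |
|---|---|---|
| Day 1 | registry enrolment (SAP 2.1.3) | first everolimus dose in M2301 (SAP 2.1.1, 2.1.3) |
| 16/17 limit applied | at Day 1 (SAP 2.3.1) | at completion of M2301 (Protocol 4.1, 5.2), with a 3-month margin (5.3) |
| Tanner condition | none in the growth FAS | not Stage V at completion of M2301 |
| End of observation | none stated | Stage V or 16/17 (Protocol 4.1, 4.3, 7.1.3) |

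**3. The interval g from first dose to M2305 enrolment.** It is not stated. A rough lower bound comes from dates in the protocol. An FDA decision of 29-Aug-2012 rested on M2301 (1.1.2), whose main outcome followed 6 months of treatment (1.2.1.2), so first doses fell by about 29-Feb-2012. Amendment 1 says M2305 enrolment had not started, and the amended text cites a decision of 15-Nov-2013. From 29-Feb-2012 to 15-Nov-2013 is 625 days, about 1.7 years. This is an inference for patients randomised to everolimus; placebo patients who started later could have less. Below, g = 4 and g = 6 are assumptions.

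**4. Highest possible age in the Year k row (girls/boys).** M2305: min(15.75 − g + k, 16) / min(16.75 − g + k, 17). TOSCA, with no stated end: (16 + k) / (17 + k).

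| Row | M2305, g = 1.7 | M2305, g = 4 | M2305, g = 6 | TOSCA |
|---|---|---|---|---|
| Baseline | 14.05/15.05 | 11.75/12.75 | 9.75/10.75 | 16/17 |
| Year 4 | 16/17 | 15.75/16.75 | 13.75/14.75 | 20/21 |
| Year 6 | 16/17 | 16/17 | 15.75/16.75 | 22/23 |

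The WHO school-age reference is "for patients aged between 5 to 19 years old". Later TOSCA heights have no SDS, and SAP 3.8.1 does not say how the last-height rate treats a patient whose last height falls there.

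**5. Illustration of the share past the limit.** Assume TOSCA entry ages uniform from 0 to the limit and follow-up to Year 4. Past 16/17 at Year 4: 4/16 = 25% of girls, 4/17 = 24% of boys. Among those still at or under 19, who can have an SDS: 3/15 = 20% of girls (entry age 12 to 15) and 2/15 = 13% of boys (entry age 13 to 15). The documents do not support uniform entry. Protocol Table 1-1 describes TOSCA as any age with TSC diagnosed within the last 12 months, so entry follows diagnosis.

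**6. What an age cut does.** Same uniform assumption in both groups, girls, ages only (Stage V not modelled). Mean age:

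| Row | M2305, g = 1.7 / 4 / 6 | TOSCA as planned | TOSCA cut at 16 |
|---|---|---|---|
| Baseline | 7.0 / 5.9 / 4.9 | 8.0 | 8.0 |
| Year 4 | 10.0 / 9.9 / 8.9 | 12.0 | 10.0 |

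The baseline entry for M2305 is (15.75 − g)/2. The Year 4 entries add 4 to the mean start age of those still under 16; for TOSCA cut at 16 that is 12/2 + 4. The planned 12.0 counts every height, including those past 19. The cut repairs most or all of the late rows and leaves the baseline row untouched, so a summary by attained age is needed as well.

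**7. Sampling noise.** With an assumed SDS standard deviation of 1, the standard error of the M2305 mean is 1/√15 = 0.26. With 10 or 7 patients left in a row it is 0.32 or 0.38.

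**The case against.** The strongest reply is that SDS is already standardised for age and sex, so different ages in a row do not by themselves bias it. That is correct, and it rules out one inference a reader might draw, that the age gap alone shifts the SDS rows. What stands is that the reference is not specific to pubertal stage, while M2305 is selected, and later depleted, on Tanner stage.

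A reader might also infer a downward drift of definite size in M2305 as early maturers leave. The documents do not support that. They give no relation between height SDS and timing of maturity. No M2305 patient can leave before M2305 enrolment, so one-sided exit acts only in rows later than g, where TOSCA's stated 4 to 6 years may offer little overlap.

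Nor do the documents support the idea that TOSCA heights at 20 to 22 years enter the SDS rows, since no reference exists there. That TOSCA continues past Stage V or 16/17 is read from silence; the registry protocol is not among the documents.

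Finally, the display is descriptive, comparison with TOSCA is a secondary objective, age at baseline is tabulated for both groups (SAP 3.2), and SAP 4.2 itself calls 15 patients too few for any comparison. All of this lowers the stakes. It does not align the rows, which SAP 2.2 and 3.8.1 still plan to print side by side.

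**Conclusion.** The concern holds in a limited form. The documents fix the mismatch: the 16/17 limit acts at Day 1 in TOSCA and after Day 1 in M2305, M2305 alone is selected on not having reached Stage V, and M2305 alone has a stated end at Stage V or 16/17. The SDS rows and the last-height abnormality rate therefore cover different ranges of attained age and maturity for any positive interval g, and a difference between columns could reflect maturity selection and not everolimus.

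Neither the size nor the direction of the effect on mean SDS can be determined from the documents. The 24-25% at Year 4 (13-20% among those who can have an SDS) is illustrative and rests wholly on uniform entry ages and on TOSCA follow-up continuing. With 15 patients, any shift may be smaller than sampling noise. This is an inexpensive improvement in how the tables can be read; it does not undermine the M2305 results themselves.

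**What to change.** In SAP 3.8.1:

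1. Add a side-by-side summary of height and BMI SDS by attained age and sex, following the by-age summary that SAP 3.8.3 already plans for endocrine values.
2. For the side-by-side SDS rows and the last-height abnormality rate, use TOSCA assessments only up to the 16th birthday (females) or 17th birthday (males). This also removes values beyond the 19-year end of the WHO reference.

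Two sensitivity displays are optional: cutting TOSCA at the first recorded Stage V where staging exists, and limiting TOSCA entry age to the observed range of M2305 ages at start of everolimus. A table note should say that neither removes the M2305 entry selection on Tanner stage. The attained-age summary does not remove it either; it aligns age only.

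The cost is SAP wording, reprogramming with data already held, and fewer TOSCA records in the later rows.
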